11.1.3 Severity of AEs

11.1.3.1 Identify the AE using the CTCAE version 4.0. The CTCAE provides descriptive terminology (MedDRA lowest level term) and a grading scale for each AE listed. A copy of the CTCAE can be found at http://ctep.cancer.gov/protocolDevelopment/electronic_applications/ctc.htm

AEs will be assessed according to the grade associated with the CTCAE term. AEs that do not have a corresponding CTCAE term will be assessed according to the general guidelines for grading used in the CTCAE v4.0. as stated below.

Grade	Severity	Description
1	Mild	Mild; asymptomatic or mild symptoms; clinical or diagnostic observations only; intervention not indicated.
2	Moderate	Moderate; minimal, local or noninvasive intervention indicated; limiting age-appropriate instrumental activities of daily living (ADL)*.
3	Severe	Severe or medically significant but not immediately life-threatening; hospitalization or prolongation of hospitalization indicated; disabling; limiting self- care ADL**.
4	Life-threatening	Life-threatening consequences; urgent intervention indicated.
5	Fatal	Death related to AE.

CTCAE v4.0 general severity guidelines:

ADL

*Instrumental ADL refers to preparing meals, shopping for groceries or clothes, using the telephone, managing money, *etc.*

**Self-care ADL refers to bathing, dressing and undressing, feeding self, using the toilet, taking medications, and not bedridden.

11.1.4 Assessment of relationship of AE to treatment

The possibility that the AE is related to study agent will be classified as one of the following: not related, unlikely, possible, probable, definite.

11.1.5 Follow-up of AEs

All AEs, including lab abnormalities that in the opinion of the investigator are clinically significant, will be followed according to good medical practices and documented as such.

11.2 Serious Adverse Events

11.2.1 DEFINITION: Regulations at 21 CFR §312.32 (revised April 1, 2014) defines an SAE as any untoward medical occurrence that at any dose has one or more of the following outcomes:

- Death
- A life-threatening AE
- Inpatient hospitalization or prolongation of existing hospitalization
- A persistent or significant incapacity or substantial disruption of the ability to perform normal life functions
- A congenital anomaly or birth defect
- Important medical events that may not be immediately life-threatening or result in death or hospitalization should also be considered serious when, based upon appropriate medical judgment, they may jeopardize the patient and may require intervention to prevent one of the other outcomes.

11.2.2 Reporting SAEs to DCP

11.2.2.1 The Lead Organization and all Participating Organizations will report SAEs on the DCP SAE Report Form found at http://prevention.cancer.gov/clinical-trials/clinical-trials-management/protocol-information-office/pio-instructions-and-tools/2012-consortia.

11.2.2.2 Contact the DCP Medical Monitor by phone or email (email is preferred) within 24 hours of knowledge of the event.

DCP Medical Monitor: [name] Chief Lung & Upper Aerodigestive Cancer Research Group Division of Cancer Prevention, NCI, NIH [name] (For FedEx, use [name]) [contact] [contact] email: [contact]

Include the following information when calling the Medical Monitor:

- Date and time of the SAE
- Date and time of the SAE report
- Name of reporter
- Call back phone number
- Affiliation/Institution conducting the study
- DCP protocol number
- Title of protocol
- Description of the SAE, including attribution to drug

11.2.2.3 The Lead Organization and all Participating Organizations will email written SAE reports to the DCP medical monitor and DCP's Regulatory Contractor CCS Associates, Inc. (CCSA; [contact]) at [contact] within 48 hours of learning of the event using the fillable PDF SAE Report Form.

11.2.2.4 The DCP Medical Monitor and CCSA regulatory and safety staff will determine which SAEs require FDA submission as IND safety reports.

11.2.2.5 The Lead Organization and all Participating Organizations will comply with applicable regulatory requirements related to reporting SAEs to the IRB/IEC.

11.2.3 Follow-up of SAE

Site staff should send follow-up reports as requested when additional information is available. Additional information should be entered on the DCP SAE Report Form in the appropriate format. Follow-up information should be sent to DCP as soon as available. SAE related to the study agent will be followed until resolved, or deemed unlikely to further resolved by the Protocol Chair, or until the subject withdraws consent for further follow-up. SAE unrelated or unlikely to be related to study agent will be followed for at least 30 days after the last dose of study agent.

12. STUDY MONITORING

12.1 Data Management

This study will report clinical data using the OnCore application from Forte Research Systems, Inc., as stated in the Master Data Management Plan. All users of the database will have appropriate education, training and experience to perform assigned tasks. The data collection and management will be done according to the Consortia 2012 DMP.

12.2 Case Report Forms

Participant data will be collected using protocol-specific case report forms (CRF) developed from the standard set of DCP Chemoprevention CRF Templates and utilizing NCI-approved Common Data Elements (CDE). The approved CRFs will be used to create the electronic CRF (e-CRF) screens in the OnCore application. Site staff will enter data into the e-CRF for transmission to DCP according to pre-established DCP standards and procedures. Amended CRF will be submitted to the DCP Protocol Information Office for review and approval. Approved changes will be programmed into the OnCore database by the Consortium Data Management staff.

12.3 Source Documents

Source documentation for this trial will consist of protocol-specific source documents as well as clinical and research laboratory reports. In the event of a Serious Adverse Event, medical records related to the event will be sought for source documentation of the event and its treatment, if any.

12.4 Data and Safety Monitoring Plan

The University of Arizona Cancer Center (UACC) Data and Safety Monitoring Board (DSMB) will ensure subject safety by coordinating, monitoring, and providing oversight for study data and subject safety for all UA Consortium clinical trials consistent with the National Institutes of Health Policy for Data and Safety Monitoring dated June 10, 1998; further guidance statement issued by the NIH on June 5, 2000, and the policy for Data and Safety Monitoring by Data and Safety Monitoring Boards. Data from this study will be monitored by the UACC DSMB every six months.

Regular monthly meetings of the UA Consortium, are used as a forum to review accrual rates, problematic issues relating to accrual and protocol implementation, AEs occurrence, follow-up, and reporting; submission of all required study reports; and progress and outcomes of laboratory analyses.

12.5 Sponsor or FDA Monitoring

The NCI, DCP (or their designee), pharmaceutical collaborator (or their designee), or FDA may monitor/audit various aspects of the study. These monitors will be given access to facilities, databases, supplies and records to review and verify data pertinent to the study.

12.6 Record Retention

Clinical records for all participants, including CRFs, all source documentation (containing evidence to study eligibility, history and physical findings, laboratory data, results of consultations, *etc.*), as well as IRB records and other regulatory documentation will be retained by the Investigator in a secure storage facility in compliance with Health Insurance Portability and Accountability Act (HIPAA), Office of Human Research Protections (OHRP), Food and Drug Administration (FDA) regulations and guidances, and NCI/DCP requirements, unless the standard at the site is more stringent. The records for all studies performed under an IND will be maintained, at a minimum, for two years after the approval of a New Drug Application (NDA). For NCI/DCP, records will be retained for at least three years after the completion of the research. NCI will be notified prior to the planned destruction of any materials. The records should be accessible for inspection and copying by authorized persons of the Food and Drug Administration. If the study is done DCP Protocol Template Version 8.5 08/31/2016

outside of the United States, applicable regulatory requirements for the specific country participating in the study also apply.

12.7 Cooperative Research and Development Agreement (CRADA)/Clinical Trials Agreement (CTA)

Not applicable.

13. STATISTICAL CONSIDERATIONS

13.1 Study Design/Description

This is an open-label, randomized cross-over study to determine whether two different doses of Avmacol® (4 tablets per day for 10-14 days; 8 tablets per day for 10-14 days) increase the detoxification of tobacco carcinogens in otherwise healthy, current smokers. Participants will serve as their own controls based on a 2 x 2 cross-over design. Specifically, each participant will have two Intervention Periods (one period taking 4 tablets per day; the other taking 8 tablets per day) with a 10-14 day washout period in between to eliminate the potential carry-over effect.

13.2 Randomization/Stratification

Each participant will be randomly assigned, based on random allocation rule, to either receiving 4 tablets per day first and then 8 tablets per day or receiving 8 tablets per day first and then 4 tablets per day to eliminate the dose sequence effect. No stratification or blocking will be performed.

13.3 Accrual and Feasibility

We plan to accrue 61 eligible participants to initiate agent intervention. With an anticipated attrition rate of 33% or less (with respect to completing the intervention and having complete endpoint data), we expect to have at least 41 participants with evaluable endpoint data. Projected accrual is 2 participants per month.

13.4 Primary Objective, Endpoint(s), Analysis Plan

The primary objective of this study is to determine whether Avmacol® increases the urinary excretion of the mercapturic acid of the tobacco carcinogen, benzene, in healthy current smokers. The primary endpoint is the change (from baseline to end-of-intervention for each Intervention Period) in the mercapturic acid of benzene after Avmacol® intervention. The changes following 4 tablets of Avmacol® per day and after 8 tablets of Avmacol® per day will be determined separately. Two-sided paired t tests will be performed to evaluate whether the changes are significantly. Bonferroni correction will be used to correct for multiple comparisons (two dose levels). With a sample size of 41 and an overall significance level of 5% (based on Bonferroni correction, i.e. a 2.5% significance level for each test), there will be at least 80% power to detect an effect size of 0.50 standard deviations. This is in line with an effect size of 0.45 standard deviations for a similar study (49).

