1.2 Secondary Objectives

- To determine whether Avmacol® increases the urinary excretion of the mercapturic acids of other tobacco carcinogens, including acrolein and crotonaldehyde;
- To determine whether Avmacol® increases the urinary excretion of the mercapturic acids of tobacco carcinogens, normalized by bio-measurement of tobacco exposure;
- To determine whether Avmacol® upregulates the NRF2 target gene transcripts in the buccal cells of current smokers;
- To evaluate for a dose-response relationship between Avmacol® and the detoxification of tobacco carcinogens and the expression of NRF2 target gene transcripts.
- To determine the relationship between systemic study agent exposure and biomarker modulation.

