8. CRITERIA FOR EVALUATION AND ENDPOINT DEFINITION

8.1 Primary Endpoint

The primary endpoint is to determine the change (from baseline to end-of-intervention for each Intervention Period) in the urinary excretion of the mercapturic acid of benzene after Avmacol® intervention. The urinary levels of mercapturic acid of benzene will be normalized by urinary creatinine levels to account for varying water content of individual urine samples. The normalized mercapturic acid of benzene at end-of-intervention will be compared with that at baseline. The changes following 4 tablets of Avmacol® per day and after 8 tablets of Avmacol® per day will be determined separately.

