8.2 Secondary Endpoints

The secondary endpoints are:

- To determine the changes (from baseline to end-of-intervention for each Intervention Period) in the urinary excretion of the mercapturic acids of acrolein and crotonaldehyde after Avmacol® intervention. Similarly, the urinary biomarkers will be normalized by the urinary creatinine levels. The changes following 4 tablets of Avmacol® per day and after 8 tablets of Avmacol® per day will be calculated separately for each tobacco carcinogen.
- To determine whether Avmacol® increases the urinary excretion of the mercapturic acids of tobacco carcinogens, normalized by bio-measurement of tobacco exposure. Bio-measurement of tobacco exposure will be assessed by the total urinary levels of nicotine and major nicotine metabolites (i.e., the sum of the molar concentrations of nicotine and major nicotine metabolites in urine). The changes following 4 tablets of Avmacol® per day and after 8 tablets of Avmacol® per day will be calculated separately for each tobacco carcinogen.
- To determine the changes (from baseline to day 4-8 and to end-of-intervention) in the NRF2 target gene transcripts, assessed by the expression of *NQO1*, in the buccal cells after Avmacol® intervention. The changes following 4 tablets of Avmacol® per day and after 8 tablets of Avmacol® per day will be determined separately.
- To determine whether there is a dose-response relationship between the Avmacol® dose and the detoxification of tobacco carcinogens and the change in the NRF2 target gene transcripts.
- To determine the relationship between systemic study agent exposure, assessed by the total urinary levels of sulforaphane and its glutathione-derived metabolites (i.e., the sum of the molar concentrations of sulforaphane and its glutathione-derived metabolites in urine), and changes in detoxification of tobacco carcinogens and NRF2 target gene transcripts.

The study also includes the following explorative endpoints:

- To determine whether the *GSTM1* and *GSTT1* genotypes are important genetic modulators of detoxification of tobacco carcinogens. The change in the urinary excretion of the mercaptoruinc acids of tobacco carcinogens will be compared between *GSTM1*-null and *GSTM1*-positive subjects and between *GSTT1*-null and *GSTT1*-positive subjects.
- To bank specimens for future research including tobacco gene signature in nasal brushing, and fixed buccal cells for nuclear morphometry.

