13.5 Secondary Objectives, Endpoints, Analysis Plans

The secondary objectives include to determine whether Avmacol® increases the mercapturic acids of acrolein and crotonaldehyde and the mercapture acids of tobacco carcinogens normalized by bio-measurement of tobacco exposure and upregulates the NRF2 target gene transcripts in the buccal cells of current smokers and to evaluate for a dose-response relationship between Avmacol® and the detoxification of tobacco carcinogens and the expression of NRF2 target gene transcripts and the relationship between systemic study agent exposure and biomarker modulation. The secondary endpoints are the changes in mercapturic acids of acrolein and crotonaldehyde levels (from baseline to end-of-intervention for each Intervention Period), the changes in mercapturic acids of tobacco carcinogens, normalized by bio-measurement DCP Protocol Template Version 8.5 08/31/2016

of tobacco exposure (from baseline to end-of-intervention for each Intervention Period) and in NRF2 target gene transcripts (from baseline to day 4-8 and to end-of-intervention for each Intervention Period) assessed by the expression of *NQO1* after Avmacol® intervention. Similar to the primary endpoint, each of the changes following 4 tablets of Avmacol® per day and after 8 tablets of Avmacol® per day will be evaluated separately. For changes in tobacco carcinogens, two-sided paired t tests will be performed to evaluate the significance of changes. For changes in NRF2 target gene transcripts, linear mixed effects models will be fitted to evaluate the significance of changes since each participant will have two changes in each Intervention Period (from baseline to day 4-8 and to end-of-intervention). Linear mixed effects models will be also fitted to determine whether there is a dose-response relationship between the Avmacol® dose and the change in carcinogen metabolites and the change in the NRF2 target gene transcripts since each participant will have more than one change for each endpoint. Spearman correlation coefficient will be calculated to evaluate the correlation between systemic study agent exposure and biomarker modulation.

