In addition, we will also explore whether the *GSTM1* and *GSTT1* genotypes are important genetic modulators of detoxification of tobacco carcinogens. This will be evaluated by comparing the change in benzene for each dose level between *GSTM1*-null and *GSTM1*-positive subjects and between *GSTT1*-null and *GSTT1*-positive subjects, respectively, using two-sided two-sample t tests. For all of the secondary and exploratory analyses, adjustment for multiple comparisons will not be performed. However, the number of comparisons will be reported and we will also cautiously interpret the findings. For both primary and secondary endpoints, two-sample t tests will be performed to evaluate whether there is a significant sequence effect (e.g. receiving 4 tablets per day in the first Intervention Period vs. receiving 4 tablets per day in the second Intervention Period). Regression techniques will be used to control for baseline levels and potential confounders if necessary. Also, if the normality assumption is violated, potential transformation will be sought or nonparametric methods such as signed rank test will be performed. For any of the endpoints, if a missing rate of >15% is observed, multiple imputation by chained equations will be performed.

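### Does section 13.4 need to name the nicotine-normalised benzene change as the sensitivity analysis for the creatinine-normalised primary test?

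*Combined protocol and SAP*

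**What the plan says.** The primary endpoint is the change in the benzene mercapturic acid from baseline to the end of each Intervention Period. Section 8.1 sets the scaling: "The urinary levels of mercapturic acid of benzene will be normalized by urinary creatinine levels", with varying water content as the stated reason. Section 13.4 gives the test, in a sentence that lacks its last word: "Two-sided paired t tests will be performed to evaluate whether the changes are significantly". Each dose is tested separately at 2.5%, with 41 evaluable participants. Section 13.1 describes the two periods as "one period taking 4 tablets per day; the other taking 8 tablets per day", so neither is untreated.

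The plan also measures smoke exposure. Section 1.2 lists as a secondary objective the effect on "mercapturic acids of tobacco carcinogens, normalized by bio-measurement of tobacco exposure". Section 8.2 defines the measure: "Bio-measurement of tobacco exposure will be assessed by the total urinary levels of nicotine and major nicotine metabolites". The same section requires the changes to be calculated separately for each tobacco carcinogen and each dose, and section 9.1 counts benzene among those carcinogens. Section 7.3 assigns the overnight urine to both the carcinogen and the exposure measurements. Section 13.5 supplies the test: "For changes in tobacco carcinogens, two-sided paired t tests will be performed to evaluate the significance of changes".

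Three further provisions in 13.5 bear on the point. On covariates: "Regression techniques will be used to control for baseline levels and potential confounders if necessary". On multiplicity: "For all of the secondary and exploratory analyses, adjustment for multiple comparisons will not be performed"; the next sentence promises to report the number of comparisons and to interpret with caution. If normality fails, a transformation or a nonparametric method such as the signed rank test is to be used.

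**The concern.** Creatinine corrects for how dilute the urine is, not for how much the participant smoked. In a before-after comparison without an untreated period, a systematic rise in smoking between baseline and end of period looks like increased excretion, and a fall can hide a real effect. Section 13.4 names no supportive analysis. The regression clause in 13.5 is conditional and names no confounder. The nicotine-normalised result sits among many unadjusted secondary results.

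If the creatinine-normalised and nicotine-normalised benzene results pointed different ways, a reader might suspect that the choice between them was made after the data were seen. At stake would be whether a significant primary result can be attributed to the agent.

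**Working it through.** **1. The plan's own figure.** Inputs from 13.4: n = 41, two-sided level 0.025 per dose, effect 0.50 SD. For a paired t test, df = 40, the critical value is 2.329 and the noncentrality is 0.50 × √41 = 3.20. Power from the noncentral t distribution is 80.5%, which agrees with the stated figure of at least 80%.

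**2. What drift would do to the primary test.** The documents give no variance for the change and no figure for changes in smoking. Assume that the mercapturic acid is proportional to smoke exposure, that the SD of the log change is 0.4, 0.5 or 0.6, and that smoking shifts by 10% in the same direction in both periods.

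| SD of log change | ln(1.10)/SD | Rejection, no agent effect, 10% rise | 0.50 + ln(0.90)/SD | Power, true 0.50 SD, 10% fall |
|---|---|---|---|---|
| 0.4 | 0.238 | 22.3% | 0.237 | 22.0% |
| 0.5 | 0.191 | 14.5% | 0.289 | 32.7% |
| 0.6 | 0.159 | 10.5% | 0.324 | 40.9% |

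If the drift occurs in Period 1 only (21 of 41 participants shifted at a given dose), the rejection rates drop to 6.8/5.2/4.5% and the powers are 49.7/57.5/61.7%.

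These figures put the primary endpoint on the log scale, which 13.4 does not specify. On the raw scale, with an assumed between-person log SD of 0.5 to 1.1, the 10% rise in both periods gives rejection in about 4 to 17%.

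**3. Whether the plan has an analysis that would show this.**

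| Needed | Where it stands |
|---|---|
| Exposure-normalised objective | 1.2 |
| Definition of the exposure measure | 8.2 |
| Separate result for each carcinogen and dose | 8.2 |
| Benzene among those carcinogens | 9.1 |
| Same urine sample | 7.3 |
| Named test | 13.5 |

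Nothing has to be added for this result to exist. Under the assumptions in step 2, the nicotine-normalised test on the log scale rejects at about its nominal 2.5% when smoking drifts and the agent does nothing.

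**4. What the label would change.** Sample size, level per test and power are the same with or without it. It would not settle conflicting results either. Let r be the correlation between the log changes of the two markers, with equal SDs. The normalised change then has SD equal to SD × √(2(1 − r)), so a 0.50 SD effect becomes 0.50/√(2(1 − r)): 0.423, 0.500 and 0.645 at r = 0.3, 0.5 and 0.7. Its power is 65%, 80% and 96%. Simulation with no drift gives:

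| r | Only primary significant | Only normalised significant | Sum |
|---|---|---|---|
| 0.3 | 21.6% | 6.0% | 27.6% |
| 0.5 | 11.4% | 11.3% | 22.7% |
| 0.7 | 2.0% | 17.5% | 19.5% |

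Disagreement on significance in 20 to 28% of trials reflects sampling variation in two imperfectly correlated tests. Calling one of them a sensitivity analysis leaves these rates as they are. A rule that both must be significant would discard true effects.

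**5. Scale of the normalised test.** Section 13.5 does not specify logs. With SD of log change 0.5 and between-person log SD of the ratio 0.5 to 1.1 (both assumed), a t test on the raw ratio has 25 to 89% power, against 65 to 96% on the log scale. However, 13.5 calls for a transformation or a nonparametric test when normality fails, for any endpoint. In these scenarios a Shapiro-Wilk check (my assumption, since the plan names none) rejects normality in more than half of trials. A log fallback then comes within about 4 points of the log test's power, and a signed rank fallback is at most about 14 points below it.

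**The case for a change.** The strongest reply is that the point concerns the role of an analysis, not its existence. Section 13.4 does not link the two results, the regression clause in 13.5 applies only if needed, and the sub-analyses in 13.8 only exclude participants with major deviations. The query on current tobacco use (Schedule of Events, footnote 11) asks only whether at least 10 cigarettes a day were smoked since the previous visit, so a fall from 30 to 20 would go unnoticed. Disagreement between the two tests is foreseeable without any drift, and one sentence would cost nothing.

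All of that is accurate as description. It does not make a defect. A concern about choosing after the data are seen needs an analysis left open, and here both the primary and the nicotine-normalised tests are fixed in advance for the same doses, visits and urine. Keeping the exposure-normalised question as a separate secondary objective is a legitimate choice. A label without a rule for conflicting results would not change how they are read, and step 4 shows why a strict rule would do harm. Reporting both results as end-to-baseline ratios would require a log-scale primary analysis, which is a change to the primary test and more than a label.

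**Conclusion.** The concern does not hold. The plan already pre-specifies the nicotine-normalised benzene change for each dose, with its own test on the same samples, and carrying out the plan gives the reader both results. Whether 13.4 also calls it a sensitivity analysis is a matter of wording that alters no estimate, error rate or sample size.

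The possible distortion of the primary test is real in principle: 10 to 22% rejection under a 10% rise in both periods with no agent effect, and 4 to 7% if the rise is confined to Period 1. These figures rest on an assumed common drift, an assumed SD and a log scale, none of which the documents supply. Entry at 10 or more cigarettes a day, periods of nominally 10 to 14 days and cessation information only after Period 2 make a common drift less likely, though they do not exclude it.

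The nicotine-normalised endpoint has limits of its own. It removes drift fully only if excretion is proportional to smoke exposure, it cannot address other time effects, and nicotine from products other than cigarettes would disturb the ratio. A sensitivity label would remove none of these limits.

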2.3 Rationale

Proof-of-concept clinical trials in healthy volunteers have shown that BSPs rich in GR and/or SF are well-tolerated and promote rapid, sustained detoxication of the airborne pollutants acrolein and benzene (33, 35-38). In preclinical studies, SF has exhibited chemopreventive activity against carcinogen-induced stomach, skin and breast cancers (43-47). Studies in $Nrf2^{-/-}$ mice have shown that the chemopreventive effect of sulforaphane against benzo[a]pyrene-induced gastric cancer and 7,12-dimethylbenz(*a*)anthracene (DMBA)-induced skin cancer depends on the NRF2 signaling pathway (43, 44, 47). The relevance of NRF2 to oral cancer chemoprevention is highlighted by the enhanced susceptibility of $Nrf2^{-/-}$ mice to oral cancer induced by the carcinogen 4-nitroquinoline-1-oxide (4NQO), and the reduced susceptibility of *Keap1*^{-/-} mice (48). We have shown that SF induces NRF2 and NRF2 target gene expression in normal oral keratinocytes and in HNSCC cell lines *in vitro*. In a preclinical chemoprevention study, we have determined that SF reduces both the incidence and total burden of oral tumors in 4NQO-treated mice. Finally, we have observed mucosal bioactivity of two well-tolerated BSPs, sulforaphane-rich BSE and Avmacol® ((39); unpublished data NCT02800265), which both upregulated transcripts for the NRF2 target gene *NQO1* in the buccal mucosa of healthy volunteers.

2-Phenethyl isothiocyanate (PEITC), another glucosinolate present in certain cruciferous vegetables including watercress and broccoli sprouts, has been demonstrated to have multiple chemoprotective effects on xenobiotic metabolizing enzymes and molecular pathways related to cancer (1, 2). In a randomized, crossover study, PEITC promoted detoxication of benzene and acrolein in a healthy smoking population (49). A much stronger effect was observed among subjects with the null genotype of both *GSTM1* and *GSTT1*. Due to established mechanisms of action, SF-rich BSPs are likely to be more effective inducers of NRF2 target genes and consequent detoxication of tobacco carcinogens in this population. Moreover, in a 300-patient study in Qidong, China, the upregulation of the urinary excretion of the mercapturic acid of benzene by broccoli sprout extracts was independent of *GSTM1* and *GSTT1* genotypes, suggesting broader applicability of this green chemoprevention strategy across a general population (38).

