13.8 Evaluation of Response

All subjects with endpoint data will be assessed for response to intervention, based on the endpoints described above in Sections 13.4 and 13.5.

Sub-analyses may be performed on the subsets of participants, excluding those for whom major protocol deviations have been identified (e.g., early discontinuation of intervention, major protocol violations, etc.). However, sub-analyses may not serve as the basis for drawing conclusions concerning efficacy, and the reasons for excluding participants from the analysis should be clearly reported.

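### Holm's step-down test in place of Bonferroni would add about 3 to 7 points of power per dose at the same 5% familywise error if both doses work equally; Section 13.4 should also give power at the 0.45 SD it cites

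*Combined protocol and SAP*

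**What the plan says.** Section 13.4 makes the change from baseline to end of intervention in the benzene mercapturic acid the primary endpoint, determined separately at 4 and at 8 tablets per day. On the test it says "Two-sided paired t tests will be performed to evaluate whether the changes are significantly", and on multiplicity "Bonferroni correction will be used to correct for multiple comparisons (two dose levels"). Overall significance is 5%, so each test is run at 2.5%. With 41 participants, "there will be at least 80% power to detect an effect size of 0.50 standard deviations". The effect size is then supported by one sentence: "This is in line with an effect size of 0.45 standard deviations for a similar study (49"). No stepwise procedure is mentioned, power at 0.45 SD is not given, and the correlation between a participant's two changes is not stated.

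Three other places bear on this:

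- Section 2.3 identifies reference 49 as a crossover study of a different compound, in which "PEITC promoted detoxication of benzene and acrolein in a healthy smoking population (49"). It then gives a reason to expect more here: "SF-rich BSPs are likely to be more effective inducers of NRF2 target genes and consequent detoxication of tobacco carcinogens in this population".
- Section 13.3 plans 61 participants starting agent, with attrition of 33% or less: "we expect to have at least 41 participants with evaluable endpoint data".
- Section 13.8 sets the analysis population: "All subjects with endpoint data will be assessed for response to intervention".

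**The concern.** There are two separate points, and the first carries the weight.

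**Choice of procedure.** Bonferroni holds both p-values to 2.5% even after one dose has been shown to work. Holm compares the smaller p-value with 2.5% and, if that is significant, the larger with 5%. The data and the tests are the same, and familywise error stays at or below 5% whatever the correlation between the tests. Holm can never declare fewer doses significant than Bonferroni. Since Sections 8.1 and 13.4 call for a conclusion at each dose, the power given up is power for the primary output.

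**The 0.45 SD benchmark.** The only empirical figure offered for the effect size is smaller than the planning value, and 41 is the smallest sample that reaches 80% at 0.50 SD. A reader of Section 13.4 could take the comparison to mean that the trial is also adequately powered at 0.45 SD. With 41 evaluable it is not.

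**Working it through.** **Inputs.** From Section 13.4: two-sided paired t test for each of two doses, 2.5% per test, 41 evaluable, effect sizes 0.50 and 0.45 SD of the change. From Section 13.3: 61 starting, at most 33% attrition, and 61 × 0.67 = 40.9, about 41. Assumed, because the documents give no value: correlation between the two changes of 0 to 0.9.

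**Step 1: reproduce the plan's figure.** For n pairs and effect d in SD units, the t statistic is noncentral t with n − 1 degrees of freedom and noncentrality d√n. Power is the probability that it exceeds the two-sided critical value in absolute size. At n = 41 the 2.5% critical value is 2.329, and the noncentrality at d = 0.50 is 0.50 × √41 = 3.20. Power is 80.5%. At n = 40 it is 79.3%. The stated 80% is correct.

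**Step 2: power at 0.45 SD under Bonferroni.** The noncentrality at n = 41 is 0.45 × √41 = 2.88.

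| Evaluable | Power per dose at 0.45 SD |
|---|---|
| 41 | 70.9% |
| 45 | 75.5% |
| 49 | 79.5% |
| 50 | 80.5% |
| 61 | 88.5% |

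Reaching 80% needs 50 evaluable, which is attrition of 1 − 50/61 = 18%.

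**Step 3: Holm, exact when the two changes are uncorrelated.** Let P₁ be power at 2.5% and P₂ power at 5%. With equal effects, Holm's power per dose is P₁ + P₁(P₂ − P₁): the dose passes at 2.5%, or it falls between 2.5% and 5% while the other dose passes at 2.5%.

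- At 0.50 SD, P₁ = 0.8048 and P₂ = 0.8778: 0.8048 + 0.8048 × 0.0730 = 0.864.
- At 0.45 SD, P₁ = 0.7085 and P₂ = 0.8028: 0.7085 + 0.7085 × 0.0943 = 0.775.

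**Step 4: Holm with correlation.** Simulated trials with n = 41, normal changes, equal effects and 1,000,000 trials per setting. Ranges run over correlations 0 to 0.9.

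| Outcome | Effect | Bonferroni | Holm |
|---|---|---|---|
| A given dose significant | 0.50 SD | 80% | 84-86% |
| A given dose significant | 0.45 SD | 71% | 75-78% |
| Both doses significant | 0.50 SD | 65-75% | 77-82% |
| Both doses significant | 0.45 SD | 50-65% | 64-73% |
| At least one significant | 0.50 SD | 86-96% | same |
| At least one significant | 0.45 SD | 77-92% | same |

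The gain per dose runs from 3.4 points (0.50 SD, correlation 0.9) to 6.7 points (0.45 SD, correlation 0). A separate simulation of 200,000 trials per setting agreed. At a correlation of 0.95 and 0.50 SD the gain falls to 2.9 points.

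**Step 5: sample size under Holm.** For 80% per dose at 0.45 SD, Holm needs 44 evaluable at correlations 0 and 0.3, 45 at 0.6 and 46 at 0.9. Those figures correspond to attrition of 1 − 44/61 = 28% down to 1 − 46/61 = 25%. With 41 evaluable, Holm does not reach 80% at 0.45 SD.

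**Step 6: unequal effects.** With assumed effects of 0.20 and 0.45 SD, the stronger dose goes from 71% to 71-72% and the weaker from 16% to 22-24%. With 0.25 and 0.50 SD, the weaker gains about 8 to 10 points and the stronger 0 to 2. If one dose has no effect, the working dose gains about 0.2 points or less.

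**Step 7: familywise error of Holm.** With no effect at either dose and no correlation it is 1 − 0.975² = 4.9%; over the simulated correlations it was 3.6% to 4.9%. With one null dose and the other at 0.45 or 0.50 SD it was 3.8% to 4.5%.

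**The case against.** The case for leaving the plan alone has real force. Bonferroni is valid and prespecified, and the sample size matches it, so nothing is being corrected. The primary objective asks whether the product increases excretion. If a rise at either dose answers that, the relevant probability is at least one significant result, which Holm leaves unchanged. The largest gain is for both doses being significant, which the plan never sets as its criterion. The 3 to 7 points also need equal effects, yet a dose-response relationship is itself a secondary objective.

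On the benchmark, Section 13.4 does not say which analyte, contrast or standard deviation the 0.45 refers to, so 71% is illustrative. It also applies at the floor of 41: each test needs only the two urine collections of its own period, all subjects with endpoint data are assessed, and Section 13.5 brings in multiple imputation when more than 15% are missing. Finally, Section 14.3 sends amendments to the sponsor and requires IRB approval, and Holm gives up simple matching intervals.

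Most of these limits stand and are part of the conclusion. They make the gain conditional, but none makes Holm worse than Bonferroni for testing in any scenario. The endpoint is reported dose by dose, so power per dose is relevant whichever reading of the objective is taken. Imputation and the amendment route do not alter the comparison between the two procedures. The loss of simple intervals is the one genuine cost.

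**Conclusion.** The point holds as an inexpensive improvement that should be made. The plan's calculation and its error control are both sound. Holm gives about 3 to 7 points more power per dose with 41 evaluable, and roughly 7 to 13 points more for both doses being significant, provided the two doses have equal effects of 0.45 to 0.50 SD and their changes are correlated between 0 and 0.9. When effects differ clearly, the benefit goes mainly to the weaker dose, which remains poorly powered at 0.20 SD.

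The power figure at 0.45 SD is a smaller matter of justification. It is 71% per dose at the planning floor and higher if more participants are evaluable. Section 2.3 contains an argument for planning on a larger effect than the comparator's, but Section 13.4 does not use it.

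**What to change.** **Main change, before any urinary results are seen.** Replace the Bonferroni sentence in Section 13.4 with:

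> The two dose-level p-values will be tested by Holm's step-down procedure at an overall 5%: the smaller is compared with 2.5% and, only if it is significant, the larger is compared with 5%.

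**Secondary change.** Replace the two power sentences with:

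> With 41 evaluable participants, power per dose under Bonferroni (a lower bound for Holm) is 80% at 0.50 SD and 71% at 0.45 SD, the effect in a study of a different compound (49).

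If 0.50 SD rests on the expectation in Section 2.3 of a stronger effect than that compound's, Section 13.4 should say so.

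**Cost.** Two sentences in an amendment, with the approvals Section 14.3 requires; no extra participants, samples or tests. Interval reporting needs a decision: a plain 97.5% interval can include zero for a dose that Holm declares significant with a p-value between 2.5% and 5%, so the plan should say which intervals will accompany the tests. The power stated at 0.45 SD will look less favourable than the present text.
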